4.3 Study Subjects

4.3.1 Disposition of Subjects

Subject disposition will be summarized for the SAF by treatment sequence and over all subjects combined. Summaries will include the number and percentage of subjects in each analysis set, completing the study, and discontinuing the study early by the primary reason for discontinuation.

4.3.2 Protocol Deviations

Major protocol violations will be summarized by treatment group for the FAS. Major protocol violations are protocol deviations captured on-study that are deemed by the Sponsor to potentially impact the efficacy or safety conclusions of the study.

All major protocol violations will be determined and appropriately categorized prior to database lock and prior to breaking the blind of the treatment group assignments. The number and percentage of subjects with any major protocol violations as well as the number and percentage of subjects with violations within each category will be presented.

4.4 Efficacy Evaluation

4.4.1 Datasets Analyzed

All efficacy summaries will be based on the FAS; select efficacy summaries will also be produced on the PPS as a sensitivity analysis. A data listing of subjects excluded from the FAS or PPS, to include the reason for exclusion, will be presented.

4.4.2 Demographic and Other Baseline Characteristics

Demographic and baseline characteristic variables will be summarized by treatment sequence and over all subjects combined for the SAF, FAS, and PPS.

Demographic variables include age, sex, ethnicity, and race. Age will be reported as collected on the eCRF and summarized using descriptive statistics. Sex, ethnicity, and race will be summarized with the number and percentage of subjects in each parameter category.

Confidential Page 18 of 28

Baseline characteristics include height, weight, body mass index (BMI), medical history, WASI-II assessment, and domain/symptom of greatest impairment. Height, weight, BMI at baseline, and WASI-II assessment scores will be summarized using descriptive statistics. The domain/symptom of greatest impairment will be determined using the subject inclusion criteria described in Section 7.1 of the clinical study protocol and is further described later in Section 4.4.7.8. The number of subjects in each category (anxiety symptoms in clinical range, anxiety symptoms in subclinical range, ADHD symptoms in clinical range [majority related to inattention], ADHD symptoms in subclinical range, and autism symptoms in subclinical range) will be summarized with frequency counts and percentages.

Medical history conditions will be mapped to preferred terms and system organ classes using the Medical Dictionary for Regulatory Activities (MedDRA, version 24.1). Frequency counts and percentages to summarize subjects reporting abnormal medical history by system organ class and preferred term will be presented.

4.4.3 Measurements of Treatment Compliance

Compliance with the study treatment regimen will be determined as the total number of doses received divided by the expected number of doses received, multiplied by 100. The expected number of doses is defined as the date of last dose of IP minus the date of first dose of IP, plus one, times two. The total number of doses received will be calculated as the number of expected doses minus the number of missed doses as reported on the *Subject Checks* eCRF. Dosing compliance will be summarized using descriptive statistics, by treatment group, based on the SAF. The number and percentages of subjects who are < 80% compliant and $\ge 80\%$ compliant within each treatment group will be summarized.

4.4.4 Primary Efficacy Endpoint Analysis Methods

The primary estimand is the difference in means between treatment groups in the CGI-I scale per central rater for all subjects in the FAS. Data collected at post-baseline evaluation time points will be combined across the two treatment periods depending on the treatment received.

The null hypothesis to be tested is that there is no difference between Placebo and NB-001:

$$H_0$$
: $\mu_A = \mu_B$;

Where μ_A and μ_B represent the mean values for Placebo and NB-001, at the end of each respective treatment period. The alternate hypothesis to be tested is that the treatment group means differ:

$$H_1$$
: $\mu_A \neq \mu_B$;

The treatment effect will be evaluated using a mixed-effects model that includes treatment, visit, treatment-by-visit interaction, period, and sequence as fixed effects, subject nested within sequence as a random effect, and the baseline CGI-S value as a covariate. The within-subject errors will be modeled using an unstructured covariance

Confidential Page 19 of 28

matrix. The Kenward-Roger approximation will be used to estimate denominator degrees of freedom. If the model fails to converge, other covariance structures will be evaluated until model convergence is met.

4.4.5 Secondary Endpoint Analysis Methods

The CGI-I per local rater, CGI-S per central rater, CGI-S per local rater, PARS Total Severity Score per central rater, PARS Total Severity Score per local rater, ADHS-RS-5 (Inattention and Hyperactivity Subscale Scores), and the SRSTM-2 Total Derived T-Score will be analyzed using the same statistical methodologies as applied to the primary efficacy endpoint, described in Section 4.4.4. For all endpoints where baseline is collected (i.e., excluding the improvement scales), the baseline value will be added as a covariate in the mixed-effects model.

The analyses for the CGI-I per central rater, CGI-S per central rater, PARS per central rater, ADHS-RS-5, and SRSTM-2 as described above will also be presented in separate summaries by treatment period. For these analyses, the mixed-effects model used to evaluate the treatment effect will include treatment, visit, and treatment-by-visit interaction as fixed effects and the baseline value as a covariate.

For all efficacy measures, mean scores over time will be plotted and presented by treatment group as well as by treatment sequence. Spaghetti plots will also be provided to show individual scores over time by treatment sequence.

For the CGI-I per central rater, scores collected during the washout and follow-up periods will be summarized by treatment sequence using descriptive statistics.

Confidential Page 20 of 28

4.4.7 Statistical/Analytical Issues

4.4.7.1 Adjustments for Covariates

For all endpoints where baseline is collected (i.e., all except the improvement scales), the mixed-effects model to compare treatment groups will include a covariate adjustment for the baseline value.

4.4.7.2 Handling of Dropouts or Missing Data

No explicit imputations will be performed on missing data; all analyses will be based on observed data only.

4.4.7.3 Interim Analyses and Data Monitoring

There are no interim analyses planned, nor is there a plan to establish a data monitoring committee for this study.

4.4.7.4 Multicenter Studies

Efficacy data collected from all study sites will be pooled for data analysis. The effect of study site on the efficacy analysis results may be explored post hoc, as needed.

4.4.7.5 Multiple Comparisons/Multiplicity

An overall treatment effect evaluation will be performed using the global test for multiple endpoints (O'Brien 1984; Dmitrienko and Tamhane 2009). This test relies on pooling the evidence of effectiveness across several endpoints. The global alternative hypothesis to be tested is that NB-001 is uniformly better than placebo in the mean changes from baseline in the PARS Total Severity Score, ADHD-RS-5 Inattention Subscale Score, and SRSTM-2 Total Derived T-Score scores when evaluated as a single instrument.

The procedure will be based on the ordinary least squares (OLS) estimate of the common effect size. In this method, the OLS test statistic will be computed using the following formula:

$$t_{OLS} = \frac{t_1 + t_2 + \dots + t_m}{\sqrt{1 + R_{11} + \dots + R_{1m} + 1}}$$

where m=3 is the number of endpoints, $t_1, t_2, ..., t_m$ correspond to the t-statistics computed for each individual endpoint score, and $R_{11}, ..., R_{1m}$ correspond to the Pearson correlation coefficients as displayed in the correlation matrix below:

$$\widehat{R} = \begin{bmatrix} 1 & \cdots & R_{1m} \\ \vdots & \ddots & \vdots \\ R_{1m} & \cdots & 1 \end{bmatrix}$$

The global one-sided p-value corresponding to this test statistic will be calculated using the Logan-Tamhane formula (Logan and Tamhane 2004), and will be considered significant at the 0.025 level.

Confidential Page 21 of 28

The data will be checked for normality and a nonparametric global testing approach will be applied if major deviations from normality are detected.

The primary efficacy analysis will be performed on the FAS; the PPS will be utilized as a sensitivity analysis. The PPS will exclude subjects with major protocol violations.

A supplemental sensitivity analysis may also be performed for subjects with efficacy assessments performed out of window for the Day 42 and/or Day 91 study visits.

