15.4. Efficacy Analyses

All statistical testing will be based on a 2-sided significance level of 0.05 and will be considered exploratory in nature. Efficacy results will be analyzed by treatment group. Data collected at

post-baseline evaluation time points will be combined across the 2 treatment periods depending on the treatment received, based on the following:

The baseline value will be the last measurement reported prior to the first dose of any IP at Day 1 during Treatment Period 1 or Day 50 during Treatment Period 2 and will be further defined in the SAP.

The treatment effect on the continuous efficacy endpoints, i.e., CGI-I and CGI-S and other efficacy endpoints, will be evaluated using mixed-effects models. A model will be defined for each endpoint to include treatment, visit, treatment-by-visit interaction, period and sequence as fixed effects, subject nested within sequence as a random effect, and the baseline value as a covariate. The within-subject errors will be modeled using an unstructured covariance matrix. The Kenward-Roger approximation will be used to estimate denominator degrees of freedom. If a model fails to converge, other covariance structures will be evaluated until model convergence is met.

Each efficacy endpoint will be first evaluated within the subset of subjects with the corresponding significant domain/symptom of greatest impairment, e.g., the treatment effect on the PARS will be assessed within the subset where the symptom of greatest impairment is anxiety. Additional analyses of the efficacy endpoints will be performed in the overall subject population.

A supportive analysis of the efficacy endpoints measured on an ordinal scale, including the CGI-I and CGI-S will be performed by comparing the treatment groups using a Wilcoxon signed-rank test at each post-baseline evaluation.

An overall treatment effect evaluation will be performed using the global test for multiple endpoints (O'Brien 1984; Dmitrienko and Tamhane 2009). This test relies on pooling the evidence of effectiveness across several endpoints and will be employed for assessing the evidence to support the global alternative hypothesis that NB-001 is uniformly better than placebo in the mean changes in the PARS, ADHD-RS-5, and SRSTM-2 scores (treated as 1 instrument).

Efficacy summaries will be based on observed data only and no explicit imputation to account for missing data will be performed.

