4.6 Determination of Sample Size

A total of 30 evaluable subjects, with 15 subjects in each treatment sequence, are planned for enrollment in this trial. The sample size is chosen to guarantee approximately 80% power for demonstrating a statistically significant treatment effect at a 2-sided alpha of 0.05 if the true mean difference (NB-001 versus placebo) for the CGI-I score at the end of each treatment period is 1 and the standard deviation is 1.25. This sample size calculation is based on the paired t-test.

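### SAP 4.4.7.5 prints the OLS global-test denominator with first-row correlations only; followed literally, it does not hold the one-sided 0.025 level unless R12 + R13 + 2·R23 is zero or negative

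*SAP*

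**What the plan says.** Protocol section 15.4 announces the test without a formula: "An overall treatment effect evaluation will be performed using the global test for multiple endpoints". SAP section 4.4.7.5 supplies the detail. It chooses the OLS version: "The procedure will be based on the ordinary least squares (OLS) estimate of the common effect size". It puts t1 + t2 + ... + tm over sqrt(1 + R11 + ... + R1m + 1), "where m=3 is the number of endpoints", and explains that R11 to R1m "correspond to the Pearson correlation coefficients as displayed in the correlation matrix below". The matrix beneath shows only its four corners: 1 and R1m on the top row, R1m and 1 on the bottom row.

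On inference the SAP says: "The global one-sided p-value corresponding to this test statistic will be calculated using the Logan-Tamhane formula". The result "will be considered significant at the 0.025 level". The degrees of freedom are not written out, and the section does not say from which data R is estimated.

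**The concern.** The statistic must be scaled by the standard deviation of t1 + t2 + t3. For three correlated statistics this involves every pairwise correlation, each counted twice. The printed subscripts name only the first row of R, so a programmer who follows them leaves out R23 and counts R12 and R13 once each. If the endpoints are positively correlated, the denominator is then too small and the global claim too easy to reach.

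The gap over R matters for the same reason. In this crossover the t-statistics are largely within-subject contrasts. Correlations of raw scores also carry between-subject variation and would in general not describe the joint distribution of the t's, even with the right denominator.

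At stake is the error rate of the test that pools PARS, ADHD-RS-5 Inattention and SRS-2 into one statement about benefit.

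**Working it through.** **Inputs**
- From SAP 4.4.7.5: m = 3, one-sided level 0.025, and the printed denominator.
- From SAP 4.6: 30 evaluable subjects, used only in the finite-sample check.
- Not in the documents: R12, R13 and R23. I assume a common correlation r and show a range, plus one unequal set.

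**Formulas**
- Variance of the numerator under the null: V = sum of all R_ij = 3 + 2(R12 + R13 + R23), or 3 + 6r for a common r.
- Squared denominator as printed, with R11 = 1: D = 1 + (1 + R12 + R13) + 1 = 3 + R12 + R13, or 3 + 2r.
- Actual one-sided level: 1 − Φ(1.960 × sqrt(D/V)).

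**Reproducing the plan's figure.** If the denominator is the full sum, D = V and the level is 1 − Φ(1.960) = 0.025 at every correlation. The stated level is therefore right for the standard OLS statistic.

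**The formula as printed**

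| r | D | V | 1.960 × sqrt(D/V) | Level | Ratio to 0.025 |
|---|---|---|---|---|---|
| −0.2 | 2.6 | 1.8 | 2.356 | 0.0092 | 0.4 |
| 0 | 3.0 | 3.0 | 1.960 | 0.0250 | 1.0 |
| 0.1 | 3.2 | 3.6 | 1.848 | 0.0323 | 1.3 |
| 0.3 | 3.6 | 4.8 | 1.697 | 0.0448 | 1.8 |
| 0.5 | 4.0 | 6.0 | 1.600 | 0.0548 | 2.2 |
| 0.7 | 4.4 | 7.2 | 1.532 | 0.0627 | 2.5 |

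In general D < V exactly when R12 + R13 + 2·R23 > 0. The level is too high in that case, correct at zero, and too low when the sum is negative.

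**Unequal correlations.** With (R12, R13, R23) = (0.5, 0.3, 0.1), D = 3.8, V = 4.8 and the level is 0.0406. Listing the same three endpoints in reverse order gives (0.1, 0.3, 0.5), so D = 3.4, V = 4.8 and the level is 0.0495. The literal statistic thus depends on which endpoint is listed first, which a pooled test should not.

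**Another literal reading.** If R11 is a misprint for R12 and both printed 1s are kept, D = 2 + R12 + R13. The level is then 0.055 at r = 0, 0.075 at 0.3 and 0.083 at 0.5.

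**Finite-sample check.** I simulated 200,000 trials of 30 paired differences, with R estimated in each. The reference was a t distribution with an assumed 0.5 × 29 × (1 + 1/9) = 16.1 degrees of freedom. The printed form gave 0.021, 0.039, 0.048 and 0.055 at r = 0, 0.3, 0.5 and 0.7. The full-sum form gave 0.022 to 0.023 throughout. The pattern matches the table, with slightly lower levels. These are not the exact error rates of the planned procedure, because the SAP does not spell out its degrees of freedom.

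**The case against.** The strongest reply is that this is a slip of notation. The SAP names the OLS method and cites its sources. The printed line opens with the first entry of the matrix and closes with the two visible entries of its last row, so it can be taken as an abbreviated sum of all entries. The first-row reading also fails as a general formula: at m = 2 it gives 3 + R12, where the correct value is 2 + 2·R12. A typesetting or conversion slip cannot be ruled out either.

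Much of this stands. The full sum may well have been intended, and nothing shows that the sponsor will compute the wrong statistic. But the printed indices do not express the full sum. The leading 1 already is R11, so writing R11 next counts it twice. A full sum with that duplicate has D = V + 1 and a level of 0.012 at r = 0 and 0.018 at r = 0.7, again not 0.025. A row-by-row sum for m = 3 would end in R23 + 1, whereas the print ends in R1m + 1. The same subscripts recur in the sentence beneath the formula. The correct statistic is reached only by overriding the text.

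Independent confirmatory programming (SAP 3.5) offers some protection, but both programmers would work from the same line.

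The limits on consequence also stand. Protocol 15.4 calls all testing exploratory, the primary objective is safety, and the primary efficacy variable, CGI-I, is not part of this test.

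**Conclusion.** The formula is wrong as printed and should be corrected. Under the literal reading, a nominal 0.025 becomes 0.025 to 0.063 for common correlations from 0 to 0.7. This assumes a normal reference, the null holding for all three endpoints, and R12 and R13 entering once each.

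A reader might infer three stronger statements that the documents do not support:
- *The error rate is roughly doubled.* That describes r of about 0.3 to 0.5. The ratio is 1.0 at r = 0 and 2.5 at r = 0.7, and the test is conservative if R12 + R13 + 2·R23 < 0. The documents give no correlations. Positive values are plausible, since the ADHD-RS-5 and SRS-2 are both completed by a parent or guardian, but this remains an assumption.
- *The planned analysis is invalid.* The documents show a faulty line in the SAP, not a faulty computation.
- *R must come from period-adjusted treatment differences.* SAP 4.4.5 analyses these endpoints with mixed models. If the t's come from those models, correlations of the model residuals would also serve. What is needed is that R matches the t-statistics.

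Nor do I rest the point on this being the only multiplicity procedure: the SAP's contents list a section 4.4.6 whose text is not in the released document.

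**What to change.** In SAP 4.4.7.5:
- Print t_OLS = (t1 + t2 + t3) / sqrt(sum over i, j of R_ij) = (t1 + t2 + t3) / sqrt(3 + 2(R12 + R13 + R23)).
- Show the full 3×3 matrix, including R23.
- Add one sentence stating that R is estimated from quantities matching the t-statistics, not from raw scores. These can be the within-subject NB-001-minus-placebo differences or the residuals of the model that produces the t's; name which. The degrees of freedom used in the p-value can be stated in the same place.

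The cost is one formula and one sentence, with no change to design, data collection or sample size. When R12 + R13 + 2·R23 is positive, the global p-value will be less favourable than under the literal formula. The change should be made before unblinding, when the SAP is due to be final.

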4.4.7.7 Active-Control Studies Intended to Show Equivalence

This study does not include an active-control product and is not intended to demonstrate equivalence between any two drug products.

4.4.7.8 Examination of Subgroups

The efficacy analyses for PARS Total Severity Score per central rater, PARS Total Severity Score per local rater, ADHS-RS-5 (Inattention and Hyperactivity Subscale Scores), and SRSTM-2 Total Derived T-Score will be first evaluated within the subset of subjects with the corresponding significant domain/symptom of greatest impairment (e.g., the treatment effect on the PARS will be assessed within the subset where the symptom of greatest impairment is anxiety). The domain/symptom of greatest impairment will be determined at baseline using the psychiatric symptoms described below (inclusion criteria # 3 in Section 7.1 of the clinical study protocol):

- a) Psychiatric symptoms in the **clinical** range for at least one of three disorders (anxiety, attention/executive deficits, and social interaction/repetitive tendencies) as demonstrated by scores at or above the following numbers on at least 1 of 3 scales:
 - PARS 5-Item Severity Score ≥ 12
 - O ADHD-RS-5 Scores of 2 or 3 on at least 6 questions, with the majority of symptoms related to inattention rather than hyperactivity
 - SRSTM-2 Derived T-Score \geq 60; or
- b) Psychiatric symptoms in the **subclinical** range for at least two of three scales:
 - o PARS 5-Item Severity Score of 10 or 11
 - o ADHD-RS-5 Scores of 2 or 3 on 4 or 5 questions, with the majority of symptoms related to inattention rather than hyperactivity
 - SRSTM-2 Derived T-Score of 55-59.

Subjects may be counted in up to three subgroups, corresponding to any clinical or subclinical symptoms they report for the PARS, ADHD-RS-5, and SRSTM-2 scales. The six possible subgroups in which a subject may be counted are listed below:

Confidential Page 22 of 28

- Subjects with Anxiety Symptoms in the Clinical Range at Enrollment
- Subjects with Anxiety Symptoms in the Subclinical Range at Enrollment
- Subjects with ADHD Symptoms in the Clinical Range (Majority Related to Inattention) at Enrollment
- Subjects with ADHD Symptoms in the Subclinical Range (Majority Related to Inattention) at Enrollment
- Subjects with Autism Symptoms in the Clinical Range at Enrollment
- Subjects with Autism Symptoms in the Subclinical Range at Enrollment

For example, if a subject reports symptoms in the clinical range for anxiety and symptoms in the subclinical range for ADHD, then this subject would be included in both the Subjects with Anxiety Symptoms in the Clinical Range at Enrollment and the Subjects with ADHD Symptoms in the Subclinical Range at Enrollment subgroups.

In addition, the analyses for the CGI-I per Central Rater and the CGI-S per Central Rater will be repeated for three subgroups of the Full Analysis Set:

- Subjects with Anxiety Symptoms at Enrollment
- Subjects with ADHD Symptoms at Enrollment
- Subjects with Autism Symptoms at Enrollment

For each of these subgroups, all subjects with any symptoms in the clinical or subclinical range at enrollment as described above in inclusion criteria # 3 in Section 7.1 of the clinical study protocol will be included in the analysis.

Additional subgroup analyses may be performed post hoc, as appropriate.

4.4.8 Plasma Concentrations

Plasma concentration measurements will be summarized in a separate report and are outside the scope of this SAP.

4.4.9 Pharmacokinetic Analysis

Pharmacokinetic analysis will be summarized in a separate report and is outside the scope of this SAP.

4.5 Safety Evaluation

Safety analysis will be carried out for the SAF, to include all subjects who receive at least one capsule of IP. Subjects who do not complete both treatment periods, for whatever reason, will have all available data up until the time of termination included in the analysis. For safety analysis presented by study visit, unless otherwise stated, the

Confidential Page 23 of 28

baseline value will be the last measurement reported prior to the first dose of any IP at Day 1 during Treatment Period 1 or Day 50 during Treatment Period 2.

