5.2. Endpoints

5.2.1. Primary Endpoint

• Type, frequency, severity, and causality of TEAEs, treatment-emergent serious adverse events (TESAEs), clinically significant changes from baseline in: laboratory tests, electrocardiograms (ECGs), vital signs, and physical examination findings during treatment with NB-001

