12.1.4. Electrocardiograms

A 12-lead ECG in triplicate will be obtained at the at the Screening Visit, Day 0, Day 42, Day 91/ET Visit, and End of Trial Visit, with the subject in a supine position following at least a 5-minute rest. The Investigator will review and report the results of each ECG; the reviews on Days 42 and 91 will include a comparison of each ECG to the baseline (i.e., Day 0) ECG. Any clinically significant abnormality should be reported as an AE, as appropriate.

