12.1.5. Laboratory Assessments

The clinical laboratory tests (chemistry, hematology, and urinalysis) that will be performed are shown in Table 5. Samples will be obtained at the Screening visit, Day 0, Day 42, Day 91/ET Visit, and End of Trial Visit.

| Chemistry | Hematology | Urinalysis | |
|----------------------------|---------------------------------|---|--|
| Alkaline phosphatase | Hemoglobin | Glucose | |
| Aspartate aminotransferase | Hematocrit | Protein | |
| Alanine aminotransferase | Mean corpuscular hemoglobin | Specific gravity | |
| Total bilirubin | Mean corpuscular hemoglobin | pH | |
| Total protein | concentration | Nitrite | |
| Albumin | Mean corpuscular volume | Bilirubin | |
| Glucose | Erythrocyte count | Urobilinogen | |
| Carbon dioxide | Leukocyte count | Ketone | |
| Blood urea nitrogen | Neutrophil count and percentage | Blood | |
| Creatinine | Lymphocyte count and | Leukocyte esterase | |
| Sodium | percentage | Other | |
| Potassium | Monocyte count and percentage | | |
| Chloride | Eosinophil count and percentage | eGFR (at Screening only; using | |
| Calcium | Basophil count and percentage | the revised Schwartz equation; Fadrowski and Furth 2011, | |
| | Platelet count | Staples et al. 2010) | |

Table 5:Clinical Laboratory Tests

eGFR = estimated glomerular filtration rate

Other laboratory tests will include serum and urine pregnancy tests (β-human chorionic gonadotropin) in females of childbearing potential, and urine drug tests (amphetamines/methamphetamines, benzodiazepines, cannabinoids, cocaine, opiates).

A sample will be collected at Screening for centralized 22q11DS genotype testing to confirm diagnostic homogeneity of the trial population. Results of this test will not be required prior to randomization of each subject as historical or local records confirming diagnosis will be adequate to establish trial eligibility.

Reports containing these laboratory test results will be generated by the laboratory performing the test. Laboratory values outside of the normal range will be assessed for clinical significance by the Investigator.

Abnormal laboratory tests may be repeated at the discretion of the Investigator or Sponsor.

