3.4.2.2 Laboratory Parameters

Clinical laboratory tests will include chemistry, hematology, and urinalysis as listed below in Table 2. Samples will be obtained at the Screening visit, Day 0, Day 42, Day 91/Early Termination (ET), and Day 119/EOT Visits.

Table 2 Clinical Laboratory Tests

Chemistry	Hematology	Urinalysis
Alkaline phosphatase	Hemoglobin	Glucose
Aspartate aminotransferase	Hematocrit	Protein
Alanine aminotransferase	Mean corpuscular hemoglobin	Specific gravity
Total bilirubin	Mean corpuscular hemoglobin	pН
Total protein	concentration	Nitrite
Albumin	Mean corpuscular volume	Bilirubin
Glucose	Erythrocyte count	Urobilinogen
Carbon dioxide	Leukocyte count	Ketone
Blood urea nitrogen	Neutrophil count and percentage	Blood
Creatinine	Lymphocyte count and	Leukocyte esterase
Sodium	percentage	
Potassium	Monocyte count and percentage	Other
Chloride	Eosinophil count and percentage	eGFR (Screening
Calcium	Basophil count and percentage	only, revised
	Platelet count	Schwartz
		equation)

Confidential Page 13 of 28

Other laboratory tests will include serum and urine pregnancy tests in females of childbearing potential, and urine drug tests.

Reports containing these laboratory test results will be generated by the laboratory performing the tests. Laboratory values outside of the normal range will be assessed for clinical significance by the Investigator. Abnormal laboratory tests may be repeated at the discretion of the Investigator or Sponsor.

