3.4.2.3 Vital Signs

Vital signs will include blood pressure (systolic and diastolic), heart rate, respiratory rate, and temperature and will be performed after the subject has been at rest in the seated position for at least 5 minutes. Vital signs will be assessed at the Screening Visit and as clinically indicated per the schedule of assessments.

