3.4.2.5 Electrocardiogram

A 12-lead ECG in triplicate will be obtained at the at the Screening Visit, Day 0, Day 42, Day 91/ET Visit, and Day 119/EOT Visit, with the subject in a supine position following at least a 5-minute rest. The Investigator will review and report the results of each ECG; the reviews on Days 42 and 91 will include a comparison of each ECG to the Day 0 ECG.

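### By default the SAP's Period 2 safety baseline is the Day 42 value, so in sequence A/P the placebo change in labs, ECG and vital signs starts from an on-NB-001 measurement

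*SAP*

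**What the plan says.** SAP 4.5 gives one baseline rule for safety analyses presented by study visit, unless otherwise stated. It reads: "baseline value will be the last measurement reported prior to the first dose of any IP at Day 1 during Treatment Period 1 or Day", the second-period day being 50. The sections on laboratory data, vital signs and ECG (SAP 4.5.4, 4.5.5.1 and 4.5.5.2) state no other Period 2 baseline. Each plans observed values and changes from baseline by visit and treatment group. Labs and ECG also get shift tables from the baseline category to the worst post-baseline value.

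The measurement schedule is:

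- **Labs:** "Samples will be obtained at the Screening visit, Day 0, Day 42, Day 91/Early Termination (ET), and Day 119/EOT Visits" (SAP 3.4.2.2; Protocol 12.1.5 agrees).
- **ECG:** triplicate recordings "will be obtained at the at the Screening Visit, Day 0, Day 42, Day 91/ET Visit, and Day 119/EOT Visit" (SAP 3.4.2.5; Protocol 12.1.4 agrees).
- **Vital signs:** "Vital signs will be assessed at the Screening Visit and as clinically indicated per the schedule of assessments" (SAP 3.4.2.3). Protocol Table 3 marks them without condition at Screening and Days 0, 42, 91/ET and 119. Footnote k makes Days 1, 14, 50 and 63 conditional on clinical indication or the Investigator's judgement.

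Footnote m to Table 3 makes Day 42 the last dosing day of Period 1 and asks for the final Period 1 assessment before the wash-out begins.

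For the Investigator's ECG review, Protocol 12.1.4 uses a different Period 2 reference: "the reviews on Days 42 and 91 will include a comparison of each ECG to the baseline (i.e., Day 0) ECG". SAP 3.4.2.5 repeats the Day 0 comparison.

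**The concern.** The Day 1/Day 50 rule suits the rating scales. Protocol 15.4 states it under efficacy, and those scales are repeated at Day 49, so each period starts from an off-treatment value. Labs, ECG and vital signs have no Day 49 assessment. Applied to them, the same rule reaches back to the end-of-treatment visit of Period 1.

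The two sequences are affected differently. In P/A the Period 2 baseline is an on-placebo value, so the NB-001 change is measured from a sensible start. In A/P it is a value after six weeks of NB-001, so recovery from any drug effect is reported as a change on placebo, in the opposite direction.

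Safety is the primary objective, and the primary endpoint includes "clinically significant changes from baseline in: laboratory tests, electrocardiograms (ECGs), vital signs, and physical examination findings during treatment with NB-001". The placebo column is the reference against which a reader judges the NB-001 changes. If half of it carries the reversal of a drug effect, it is not a clean placebo reference.

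**Working it through.** The plan gives no effect size for labs, ECG or vital signs, so there is no stated figure to reproduce. The check is to locate the baseline value and then follow an assumed drug shift through the summaries.

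**Step 1: which value is the Period 2 baseline?** The last scheduled lab or ECG value before the Day 50 dose is Day 42, a dosing day. Vital signs also default to Day 42, unless a clinically indicated Day 50 reading is taken before the dose. SAP 4.1.2 lets unscheduled values count when baseline is determined, so a wash-out value could replace Day 42 in some subjects.

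**Step 2: inputs.**
- Allocation is 1:1 (SAP 3.3.2), so A/P is about 17 of 34 randomized, or 15 of 30 evaluable.
- d = true shift after six weeks on NB-001 (assumed).
- g = share of d present in the value used as the A/P Period 2 baseline (g = 1 if fully on drug).
- r = share of d still present at Day 91 in A/P (r = 0 if fully reversed).
- Placebo has no effect, and there is no drift over time in the base case.

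**Step 3: change from baseline under the SAP rule.**
- NB-001: A/P Period 1 is d and P/A Period 2 is d. Mean = (d + d)/2 = d.
- Placebo: P/A Period 1 is 0 and A/P Period 2 is rd - gd. Mean = 0.5(r - g)d.
- Gap (NB-001 minus placebo) = d - 0.5(r - g)d = d[1 + 0.5(g - r)].

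**Step 4: the same with Day 0 as baseline in both periods.**
- NB-001 mean = d. Placebo mean = (0 + rd)/2 = 0.5rd. Gap = d(1 - 0.5r).

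| Case | Placebo mean, SAP rule | Gap, SAP rule | Placebo mean, Day 0 | Gap, Day 0 |
|---|---|---|---|---|
| r = 0, g = 1 | -0.5d | 1.5d | 0 | d |
| r = 0, g = 0.5 | -0.25d | 1.25d | 0 | d |
| r = 0, g = 0 | 0 | d | 0 | d |
| r = 1, g = 1 | 0 | d | 0.5d | 0.5d |

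As an illustration of the first row, a true shift of 10 units would be tabulated as +10 on NB-001 and -5 on placebo, a gap of 15. From Day 0 it would be +10, 0 and 10.

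**Step 5: does drift over time change this?** Take r = 0 and g = 1, with an illustrative drift of 0.3d by Day 42 and a further 0.2d by Day 91.
- SAP rule: NB-001 = (1.3d + 1.2d)/2 = 1.25d. Placebo = (0.3d - 0.8d)/2 = -0.25d. Gap = 1.5d.
- Day 0: NB-001 = (1.3d + 1.5d)/2 = 1.4d. Placebo = (0.3d + 0.5d)/2 = 0.4d. Gap = 1.0d.

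Drift moves both columns but leaves the gap unchanged.

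**Step 6: is reversal plausible?** Protocol 4.3.1 gives a half-life of about 4 hours in healthy adult males. After 24 hours, 0.5^(24/4) = 1.6% of the drug remains, and Day 91 is 49 days after Day 42. This makes r near 0 plausible, but clearance of the drug does not prove that its effect has reversed.

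**The case against.** Several points on the other side stand and limit the finding.

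- **The rule covers by-visit analyses only.** The shift tables use the worst post-baseline value, which is not a by-visit summary. A reader might infer that the placebo shift tables are specified to start from drug-altered categories. The SAP does not say so: their Period 2 baseline is unspecified, and the problem arises there only if the by-visit rule is carried over.
- **The NB-001 column is sound.** The primary endpoint concerns changes during NB-001 treatment, and in the model above the baseline effect falls only on the placebo column. Adverse events are assigned by onset date (SAP 4.5.2) and do not use this baseline.
- **No formal safety contrast is planned.** The tables are descriptive. They also show observed values, which need no baseline, and abnormal labs are listed by subject.
- **Day 42 is a default, not a certainty.** A pre-dose Day 50 vital-signs reading or an unscheduled value would take precedence. The visit window of plus or minus 3 days could also place a Day 42 visit on Days 43 to 45, off drug, although footnote m asks for it before the wash-out.
- **The ECG references differ without being incompatible.** One governs the Investigator's review of individual recordings and the other the aggregate tables. Both can be followed.
- **Day 0 has its own weakness.** If an NB-001 effect persisted fully to Day 91, a Day 0 baseline would halve the gap to 0.5d, while the SAP rule would give d. Persistence that long after a drug with a short half-life seems less likely, but a safety analysis should not assume it away.

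None of this removes the main point: for the by-visit change tables, the stated rule combined with the schedule gives an on-NB-001 starting value for the A/P placebo change.

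**Conclusion.** The concern holds for the by-visit change-from-baseline tables for labs and ECG as scheduled, and by default for vital signs. With full reversal by Day 91, equal sequences and no placebo effect, the mean placebo change lies between 0 and -0.5d and the descriptive gap between 1.0d and 1.5d. The 50% excess is the upper end and requires the full shift to be present in the baseline value. The documents give no value for d, so the absolute size is unknown.

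A reader might go further and infer that the NB-001 safety results are wrong, or that a test of NB-001 against placebo is inflated. The documents support neither inference, since only the placebo reference moves and no such test is planned. The severity is should-fix: the rule can mislead about the primary objective, but it acts only through descriptive summaries.

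**What to change.** In SAP 4.5, define the baseline for labs, ECG and vital signs in both periods as the last value before the first IP dose on Day 1, normally Day 0. Apply it to the by-visit change tables and state it explicitly for the lab and ECG shift tables. Keep the Day 49 baseline for the efficacy scales. This also brings the ECG tables into line with the Day 0 reference in Protocol 12.1.4 and SAP 3.4.2.5.

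As support, show Period 2 changes by sequence from both Day 0 and Day 42. A reversing effect and a persisting one then look different in A/P, and the reader need not rely on either assumption.

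The cost is a few sentences before database lock, a changed baseline flag and a small set of supporting tables, with no new data. There are two downsides. Period 2 changes would span 91/7 = 13 weeks instead of 49/7 = 7 weeks, for both treatments alike. The Day 0 baseline would also understate the gap if an effect persisted, which the by-sequence display would reveal.
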